- 2. Subjects will be given a diary card by the study staff to mark each use of the study drug in between site visits to the study site. This is to help subjects track study drug use. Subjects will be instructed to return study drug nasal spray bottles, used or unused, to the site at each visit along with the diary card.
- 3. Each bottle will re-weighed after return to estimate the amount of fluid remaining

STUDY DRUG:

Intranasal oxytocin is FDA approved as a lactation aid and was commercially marketed (Syntocinon®, Novartis) in the US up to the 1990's. It continues to be marketed commercially by Novartis in Europe and elsewhere. Oxytocin powder (Pictocin, Novartis) is readily available in the US and is used for intravenous

administration as a paruition stimulant in pregnant women. Both intravenous and intranasal oxytocin are well tolerated and safe (Hoover RT 1971) (see risk section of this Research Plan).

This study will use oxytocin powder supplied by Spectrum Laboratories and UCSD Investigational Drug Service (IDS) will make formulate both the Oxytocin and Placebo.

-Chlorbutanolhemihydrat 2.5mg -Methyl-4-hydroxybenzoat 0.4mg -Propyl-4-hydroxybenzoat 0.2mg -Dinatriumphosphatanhydricum 1.9mg -Acidumcitricumanhydricum 2.56mg 5.0mg -Na-Sorbit -Sorbitol 70% 25.0 mg -Glycerin 85% 25.0mg -Aqua pur. q.s.

Comment: 1 IU is 1.7 micrograms oxytocin and 1 puff is 12 IU (=20.4 micrograms oxytocin)

STATISTICAL CONSIDERATION

Our primary analysis will be the comparison of subjects on oxytocin with subjects on placebo using a mixed model repeated measures analysis (MMRM). If this comparison is statistically significant then we use a linear contrast to investigate the dose-response between 84 IU (42 IU bid) and 168 IU (84 IU bid). We also have introduced an adaptive design that is consistent with FDA guidance for phase 2 studies when dosing groups are unclear (2010).

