Sample Size Calculation. The primary efficacy measure will be change in PANSS total score from baseline to each visit. Based upon a preceding proof-of-concept study (Feifel et al. Biological Psychiatry, in press) with effect sizes (cross-over design) range from .40 to .53. An estimated sample size of 24 in the placebo group and 48 in the oxytocin group (24 in each dose group) is required to achieve 85% power to detect an effect size of 0.3 for time-averaged main treatment effect (Cohen's d for standardized mean difference between oxytocin and placebo treatment groups) using 6 repeated measurements having a AR(1) (first order autoregressive) covariance structures and assuming the correlation between observations on the same subject is 0.5, and the alpha level (Type I error rate) is 0.05 in a 2-sided test (Hintze, 2008). If we ignore the repeated measures design, an effect size of 0.5 will be detected with the same alpha and beta for the same sample size of 80 patients in the ratio of 2:1 for oxytocin:placebo.

The proposed sample size includes considerations for a single pre-specified, planned interim analysis for futility stopping based on conditional power (CP) (stochastic curtailing method) (Halperin et al., 1982; Lan et al., 1982) or an equivalent stopping boundary on interim Z-test value (B-value) (Lan and Witts, 1988). This interim futility analysis will be performed and reviewed by an external statistical consultant [name] when 50% of the enrolled patients complete 6 weeks of follow-up. The adjusted critical value for an overall alpha of 0.05 (2-sided) in the final analysis is 0.0515 with resulting power 84.6% to detect a specified effect size of 0.3 or greater with 80 patients in the ratio of 2:1 for oxytocin:placebo (See Interim Analysis Plan below).

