Futility Interim Analysis Plan. This randomized, double-blind study adopts an adaptive design with a single pre-specified, planned, unblinded interim analysis for futility stopping based on conditional power (CP) (stochastic curtailing method) (Halperin et al., 1982; Lan et al., 1982) or an equivalent stopping boundary on interim Z-test value (B-value) (Lan and Witts, 1988). The purposes of this formal interim analysis are to assess CP levels which are the probability of reaching statistically significant treatment difference at study end given the interim results. To avoid inflation of Type I error, no early stopping for efficacy is planned in this study. The unblinded data will be only available to external statistician [name] and not the PIs or other study staff.

It is well known that futility termination will reduce the Type I error rate (alpha) and inflate the Type II error rate (beta =1 minus power of the test), with the level of beta inflation bounded by P_{L0} , the probability of stopping for futility under the null hypothesis of no treatment effect (Lan et al., 1982; Lachin 2005). In order to maintain the design Type I error rate (alpha) at 5% and power close to 85%, we use an iterative procedure to determine the CP utility boundary values and the adjusted Z-test critical value in the final analysis, with 60% (P_{L0}) chance of stopping for futility under the null hypothesis. This provides: 1) a CP futility stopping boundary value equal to 0.3 at 50% enrollment (i.e. stop the trial if CP observed < 0.3) under the original design assumption (see Sample Size Calculation), 2) an adjusted Z-test critical value of 1.947 (ZF) for declaring significant treatment effect in the final analysis (or $P \le 0.0515$), and 3) an overall power of 84.6%, i.e. 15.4% overall Type II error rate with 3.1% false negative error rate at interim look and 12.3% probability of continuing the trial and failing to reject the null hypothesis (false negative error rate) at study end.

In summary, we provide the following futility stopping rule for assessing interim results at 50% enrollment:

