Analysis Methods: The primary population for efficacy analyses includes all randomized subjects based on the intention-to-treat principle. The population for safety analyses will include all subjects who receive at least one dose of study medication. In the primary analysis, we test the hypothesis of difference in PANSS total change score (Week 6) between the combined oxytocin and placebo groups with adjustment for baseline score using a likelihood-based mixed-effects model for longitudinal data analysis (MMRM LDA) (Fitzmaurice and Ware, 2004). The MMRM LDA model can accommodate incomplete data under the assumption of ignorable attrition (see below under Missing Data). The same MMRM LDA model will be applied to evaluate the dose-response relationship using a linear contrast for the placebo and oxytocin dose groups, comparisons of treatment groups over time using treatment-by-visit (categorical visit variable) interaction term, and the trajectories of treatment responses over time based on time slope computed for each subject (continuous time variable).

Secondary efficacy measures will be the PANSS positive symptom and negative symptom subscales, PANSS general psychopathology subscale, CGI-S, CGI-I HAM-A, CCDS, GAF, cognitive scales as with the primary endpoint using the same MMRM LDA analyses. No multiplicity adjustment will be made in the secondary analyses. Appropriate descriptive statistics with 95% confidence intervals will be provided within and across treatment groups. Normal assumption will be checked and nonparametric alternatives will be considered if the assumption is seriously violated.

Mediators and baseline moderators of treatment effects on efficacy outcome measures will also be explored (Kraemer et al., 2006). The significance of moderator effects due to baseline characteristics (age, gender, initial

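### The stated 85% power for a time-averaged effect of 0.3 does not follow from the plan's own inputs, which give about 48–50%

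*Combined protocol and SAP*

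**What the plan says.** All of this is in Section 9, under Statistical Consideration.

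- **Main power claim (Sample Size Calculation).** 24 placebo and 48 oxytocin patients (24 per dose) "is required to achieve 85% power to detect an effect size of 0.3 for time-averaged main treatment effect". The effect is defined as Cohen's d for oxytocin against placebo. There are six AR(1) measures with correlation 0.5, and alpha is two-sided 0.05.
- **Without repeated measures.** "an effect size of 0.5 will be detected with the same alpha and beta for the same sample size of 80 patients", split 2:1.
- **After the futility look.** A final significance level of 0.0515, "with resulting power 84.6% to detect a specified effect size of 0.3 or greater with 80 patients".
- **Prior evidence.** A proof-of-concept study "with effect sizes (cross-over design) range from .40 to .53".
- **Futility Interim Analysis Plan.** "a CP futility stopping boundary value equal to 0.3 at 50% enrollment", a final critical value of 1.947, a 60% chance of stopping under the null, and "an overall power of 84.6%, i.e. 15.4% overall Type II error rate with 3.1% false negative error rate at interim look". The stopping rule then gives interim Z = 0.253 as equivalent to the conditional-power (CP) boundary, and sets the final analysis at N=72.
- **Analysis Methods.** In the primary analysis "we test the hypothesis of difference in PANSS total change score (Week 6) between the combined oxytocin and placebo groups".

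**The concern.** The inputs to the power statement are all given, so it can be checked directly, and 85% looked far too high for 72 patients and an effect of 0.3. The sentence on d=0.5 needs no covariance assumption and looked too high as well.

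Section 6 presents the trial as a pilot that will inform full-scale studies. If the true power is near one half, a non-significant result read against 85% would count as evidence against an effect that the trial had about an even chance of missing. The futility rule is calibrated on the same premise, so its error rates would be wrong too.

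**Working it through.** **1. What 85% would require.** Two-sided 0.05 with 85% power needs a drift of 1.960 + 1.036 = 2.996. With d=0.3 and 1/24 + 1/48 = 0.0625, the time average must have variance (0.3/2.996)²/0.0625 = 0.160, in units of the per-visit variance. Six fully independent measures give 1/6 = 0.167, so Z = 2.939 and power is 83.6%. No non-negative correlation therefore reaches 85% at N=72. At N=80 the AR(1) correlation would have to be about 0.04.

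**2. The stated inputs.**
- Simple mean of six AR(1) measures, correlation 0.5: variance = [6 + 2(5×0.5 + 4×0.25 + 3×0.125 + 2×0.0625 + 0.03125)]/36 = 0.3906.
- SE = √(0.3906 × 0.0625) = 0.15625; Z = 0.3/0.15625 = 1.92; power = Φ(1.92 − 1.96) = 48.4%.
- Likelihood (GLS) weighting: variance 0.375, SE 0.1531, Z = 1.96, power 50.0%.
- With the t distribution: 47.4% and 48.9%.

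**3. Other readings of the main claim.**

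| Reading | Power for d=0.3 |
|---|---|
| N=80 | 53–54% |
| Baseline-adjusted AR(1), N=72 | 51–55% |
| Baseline-adjusted AR(1), N=80 | 55–59% |
| One-sided 0.05, N=72 | 61–62% |
| Compound symmetry 0.5, N=72 | 35% |

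None of these allows for dropout. For 85% power at 24 vs 48, the detectable d is 2.996 × 0.1531 = 0.459 to 2.996 × 0.15625 = 0.468 (about 0.44 at N=80). For d=0.3, 85% would need 57 + 114 = 171 to 59 + 118 = 177 patients.

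**4. The d=0.5 sentence.** At N=80 split 2:1, the SE is √(1.5/26.67) = 0.237, Z = 2.108 and power is 55.9%. At N=72, Z = 2.0 and power is 51.6%.

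**5. The interim figures.** Take information 0.5, boundary Z = 0.253, final critical value 1.947, and the combined test alone. The interim and final Z have means θ√0.5 and θ, and correlation √0.5.

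| | θ = 2.996 | θ = 1.92 |
|---|---|---|
| Interim Z below 0.253 | 3.1% | 13.5% |
| Continue, then fail | 12.3% | 38.5% |
| Overall power | 84.6% | 48.1% |

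The plan's 3.1%, 12.3% and 84.6% reproduce exactly at θ = 2.996, which is 85% power taken as given. Under the null, Z < 0.253 has probability 60%, and upper-tail rejection is 2.5%. Those two figures do not depend on the drift, and they hold for the combined test.

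**6. CP against Z.** CP = Φ{(0.7071·Z + 0.5θ − 1.947)/0.7071}.
- At θ = 2.996, Z = 0.253 gives CP 0.35. CP 0.30 falls at Z = 0.11, where the null crossing probability is 54%, not 60%.
- At θ = 1.92, Z = 0.253 gives CP 0.13. CP 0.30 falls at Z = 0.87, which is crossed with probability Φ(0.871 − 1.358) = 31% under d=0.3.
- The two boundaries agree only near θ = 2.80, the drift for 80% power.

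**7. The basis of the power statement.** The effect of 0.3 is tied to 72 patients in one sentence and to 80 in the post-interim sentence; the d=0.5 sentence also uses 80. Section 4 and the final stopping-rule item use 72. The calculation is for a time average. Analysis Methods tests the Week 6 change, for which no effect size or power is given.

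**The case against.** **The shortfall is specific to 0.3.** The design may have been sized with the pilot effects in mind. If 0.40 to 0.53 are taken as between-group d (an assumption, since they come from a cross-over), power at N=72 is about 73% to 92%. This is fair and belongs in the plan. It does not support the sentence as written, which names 0.3.

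**Some readings come close to 85%.** Zero correlation gives 83.6% at N=72 and 87.3% at N=80. Reading 72 or 80 as per-group sizes gives 82–87% for d=0.3 and 85–89% for d=0.5. Each contradicts a stated input: the correlation of 0.5, the 24/48 split, or 80 patients in a 2:1 ratio.

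**The interim figures are right for their premise.** Overall power after a futility look is always conditional on an assumed drift. That stands. The 84.6% is a consequence of the main error, not a second one.

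**The CP mismatch is small at the plan's own drift.** Z = 0.253, B = 0.179, the drift estimate of 0.358, P = 0.800 and 60% null stopping agree with one another; only the CP value is out of line. Moving to CP 0.30 changes false stopping from 3.1% to 2.2% and power from 84.6% to 84.8%. On its own this is a minor correction. It still has to be made, because an interim Z between 0.11 and 0.253 stops on one scale and continues on the other, and the corrected drift widens the gap.

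**Rule 1a has its own target.** The stopping rule applies first to the combined comparison. Rule 1a then checks each dose and states an adjusted power of 80%. The 13.5% is therefore the chance that the combined test crosses the Z boundary, not the chance that the trial stops. On one reading (12 per arm at the interim, equal dose effects, stopping only if the combined test and both doses have Z < 0.253, no reallocation), simulated full stopping is 7.3% at drift 1.92, 1.4% at 2.996 and 44% under the null. The documents do not fix those choices, so these figures are only illustrative.

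**Conclusion.** The concern holds and the power statement must be corrected. On the plan's own inputs, power for a time-averaged d=0.3 is about 48–50% at N=72 and 53–54% at N=80, roughly 35 and 31 points below the stated 85%. The d=0.5 sentence falls about 29 points short. No reading that keeps every stated input reaches 85%. These figures use the normal approximation and assume no dropout; missing data would lower them.

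The drift-dependent interim figures inherit the error. The 72/80 split, the time-average versus Week 6 mismatch and the CP/Z disagreement are separate inconsistencies. They do not explain the gap, but they leave the power statement without a fixed basis.

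**What to change.** 1. Restate the power as about 48–50% for a time-averaged d=0.3 at N=72, with 85% only at d of about 0.46–0.47. Add that the pilot range 0.40 to 0.53 would give about 73% to 92% if taken as between-group d, and label that an assumption.
2. Delete or correct the d=0.5 sentence (56% at N=80).
3. Use one primary contrast, time-averaged or Week 6, in Statistical Consideration, Sample Size Calculation and Analysis Methods, and give the effect size and power for it.
4. Reconcile N=72 with N=80 throughout.
5. Recompute the drift-dependent interim figures from the corrected drift, and reconcile the CP and Z boundaries so that the futility rule is stated on one scale.
6. Say whether 60%, 3.1%, 12.3%, 84.6% and the critical value 1.947 refer to the combined test alone or include rule 1a, and how they relate to rule 1a's adjusted power of 80%.

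The cost is revised wording and a re-run of the calculation. No patients are added, but the stated power becomes less favourable.

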4. ESTIMATED DURATION OF THE STUDY

Study enrollment will occur over approximately a two year period. Completion of the entire protocol, including subject recruitment, study procedure execution, and statistical analysis is anticipated to take no longer than four years.

Each subject will be enrolled for a 7 week period, including a screening phase. Study procedures involve weekly clinic visits as an outpatient. Approximately 72 patients will be randomly assigned to either 84 IU of oxytocin (equivalent to 42 IU BID), 168 IU of oxytocin (84 IU BID) or vehicle placebo. The doses of oxytocin are based upon previous studies in humans showing improvement in schizophrenia related changes in behavior and brain function (Kosfeld et al, 2005; Kirsch 2005; Heinrich M 2003).

The total study duration for each individual subject will be approximately 7 weeks, which includes a 7-day screening period, a baseline (randomization) visit, and the six-week treatment phase.

Participants will remain on their current antipsychotic medication and dose throughout the study.

5. LAY LANGUAGE SUMMARY OR SYNOPSIS (no more than one paragraph)

The purpose of this study is to test whether or not people with schizophrenia feel improvement in their symptoms when oxytocin nasal spray is added to their current medications. Volunteers will be randomly assigned to one of three groups; a higher dose group, a lower dose group, or a group who receives a nasal spray with no medication in it (placebo). Volunteers will be asked questions about their mental and physical health as well as take several computer tests to track any changes over the 7 weeks of the study.

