9. RESEARCH DESIGN AND METHODS

OVERVIEW:

The proposed study is a randomized, double-blind, placebo-controlled study of the value of adjunctive intranasal oxytocin added to existing antipsychotic treatment compared with adjunctive placebo in subjects with schizophrenia. Enrolled subjects will be randomized and receive 6 weeks of treatment with one of the following adjunctives to a stable antipsychotic regimen: 1) intranasal oxytocin (84 IU/day), intranasal oxytocin (168 IU/day) or intranasal placebo. The study will be conducted over 2 years. Approximately seventy-one subjects will be entered into the study, on average 35/36 at each site each year.

PRIMARY OUTCOME MEASURE:

Positive and Negative Syndrome Scale (PANSS): The three subscales of the PANSS include the Positive scale (7 items), the Negative scale (7 items), and the General Psychopathology scale (16 items). The total PANSS score is the sum of all 30 items of which each item is scored on a 1-7 rating system (7 indicating the worst symptoms). The items on the PANSS focus on symptoms that are common in patients with psychotic disorders and include hallucinations, delusions and disorganization as well as mood disturbances.

SECONDARY OUTCOME MEASURES WILL INCLUDE:

Global Assessment of Functioning (GAF): The GAF considers psychological, social, and occupational functioning on a hypothetical continuum of mental health illness. Scores on the GAF range from 1 (extremely severe) to 100 (superior functioning).

Clinical Global Impression-Severity of Illness (CGI-S): The CGI-S is used to evaluate changes in overall severity of illness. Scores range from 1 (not at all) to 7 (among the most extremely ill).

Clinical Global Impression-Global Improvement (CGI-I): The CGI-I is a global assessment to evaluate the subject's improvement or worsening from baseline. Scores on the CGI-I scale range from 1 (very much improved) to 7 (very much worse)

Calgary Depression Scale for Schizophrenia (CDSS) is a ten item diagnostic questionnaire intended to assess the severity of depression symptoms experienced by a given patient. The CDSS will be administered by a trained and qualified rater at each scheduled study visit.

Hamilton-Anxiety Scale (HAM-A): The HAM-A is a clinician administered scale for the evaluation of anxiety symptoms. The HAM-A consists of 14 items of which each item is scored 0 (not present) to 4 (very severe).

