- 1. A recommendation to stop the trial for futility if CP value for comparing combined oxytocin vs. placebo (i.e. the probability that final study results will be statistically significant given interim data) is less than 30% under the original design assumption. An equivalent boundary for interim Z-test value is 0.253 (interim P>0.800), interim B-value ≤ 0.179, or if equivalently interim drift parameter estimate ≤ 0.358.
 - a. If futility stopping criteria are met for the combined oxytocin group, we will examine CP and interim Z-test value for each dose (vs. placebo) to check if both dose groups meet a similar stopping criterion CP <0.3 (or P>0.800) for an overall alpha of 5% and an adjusted power of 80%.
 - b. In case of dropping only 1 dose arm and reallocation of remaining subjects to another arm we will use a fixed weighted Z-test method to protect the Type 1 error (Cui et al., 1999; Lan et al., 2005).
- 2. To declare the treatment effect significant if p-value computed at study end (N=72) is less than 0.0515.

This futility interim monitoring plan will include a vigorous data quality control to ensure successful signal detection in potential treatment effects. In addition to verifying validity of study design assumptions using the unblinded interim data, we will perform blinded, ongoing assessments of inconsistencies in the efficacy outcome measures, inter-relationships between efficacy variables, missing data patterns, and will implement a data management plan that has real-time capability to detect, query, and address data issues in the study.

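### The single futility look is timed in two ways and the planned sample size is given as both 72 and 80, while the boundary figures fit only a look at exactly half information; a minor point, to be settled in the text

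*Combined protocol and SAP*

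**What the plan says.** All of this is in section 9 of the combined protocol and SAP unless stated otherwise.

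- **Trigger.** The Sample Size Calculation puts the look "when 50% of the enrolled patients complete 6 weeks of follow-up". The Futility Interim Analysis Plan gives "a CP futility stopping boundary value equal to 0.3 at 50% enrollment" and introduces its rules as a "futility stopping rule for assessing interim results at 50% enrollment". No patient count or information fraction is stated.
- **Sample size.** Section 4 says "Approximately 72 patients will be randomly assigned". The Sample Size Calculation first gives 24 placebo plus 48 oxytocin, which is 72. It then refers to "the same sample size of 80 patients in the ratio of 2:1 for oxytocin:placebo" and attaches the 84.6% power to 80 patients. Item 2 of the stopping rule returns to 72 at study end. The Overview says "Approximately seventy-one subjects will be entered into the study", and section 10 gives about 71 for the site.
- **Boundaries.** The lead rule is to stop if CP is below 30% under the original design assumption. Item 1 then states: "An equivalent boundary for interim Z-test value is 0.253 (interim P>0.800), interim B-value ≤ 0.179", and adds a drift estimate of 0.358.
- **Operating characteristics.** A 60% chance of stopping under the null, a final critical value of 1.947, a 3.1% false-negative rate at the look, 12.3% at the end, and 84.6% power.
- **If the look falls elsewhere.** The plan gives no rule for recomputing the boundaries.

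**The concern.** The two triggers are different dates. When half the sample has enrolled, the most recent entrants have up to six weeks of treatment still to run, so fewer than half have Week 6 data. Half of 72 is 36 and half of 80 is 40, so the count needed for the look is also open.

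This is the trial's only formal stop-or-continue decision. If the look does not fall at half information, boundaries that the plan calls equivalent separate, and the stated error rates are no longer exact. The external statistician would then have to decide which boundary governs with unblinded results in hand, and pre-specification is meant to prevent that.

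**Working it through.** **Inputs from the documents.** Two-sided alpha 0.05; design power 85%; interim Z 0.253; final critical value 1.947; N of 72 or 80; accrual over about two years, taken as 104 weeks; six weeks of follow-up.

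**Assumptions.** Accrual is even. Information is proportional to the number of completers.

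**Formulas.** Let t be the information fraction and θ = 1.960 + 1.036 = 2.996 the design drift.

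- B = Z√t; drift estimate = B/t
- Interim false-negative rate = Φ(0.253 − θ√t)
- CP = 1 − Φ[(1.947 − B − θ(1 − t))/√(1 − t)]
- Power = P(Z₁ > 0.253 and Z₂ > 1.947), bivariate normal with means θ√t and θ and correlation √t

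**Step 1: reproduce the plan at t = 0.5.**

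- Chance of stopping under the null: Φ(0.253) = 0.60. Stated: 60%.
- B = 0.253 × 0.7071 = 0.179; drift = 0.179/0.5 = 0.358. Both as stated.
- Interim false-negative rate: Φ(0.253 − 2.1185) = Φ(−1.87) = 3.1%. As stated.
- Power 84.57%, leaving 100 − 84.57 − 3.10 = 12.3% for the final look. As stated.
- CP at Z 0.253: 1 − Φ[(1.947 − 0.179 − 1.498)/0.7071] = 1 − Φ(0.382) = 0.351. **Not the stated 0.30.** Under the 85%-power drift, CP below 0.3 means Z below 0.11. An 80%-power drift of 2.80 would give CP 0.302.

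The plan's own numbers also fix t: 0.179/0.358 = 0.50 and (0.179/0.253)² = 0.50.

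**Step 2: where the look could fall.**

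- Half enrolment of 72: 72/104 = 0.692 per week; 0.692 × 6 = 4.2 still in follow-up; 36 − 4.2 = 31.8 completers; t = 31.8/72 = 0.44.
- 36 completers of 72: t = 0.50.
- Look set from the 80-patient figure, final analysis at 72: t = 40/72 = 0.556.

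**Step 3: what changes.**

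| t | Power, Z 0.253 fixed | Interim false-negative rate | Z implied by B 0.179 | Z implied by drift 0.358 | CP at Z 0.253 | Z at CP 0.3 | Null stopping chance, CP rule |
|---|---|---|---|---|---|---|---|
| 0.44 | 84.0% | 4.1% | 0.269 | 0.238 | 0.44 | −0.17 | 43% |
| 0.50 | 84.6% | 3.1% | 0.253 | 0.253 | 0.351 | 0.11 | 54% |
| 0.556 | 84.9% | 2.4% | 0.240 | 0.267 | 0.26 | 0.36 | 64% |

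The Z, B and drift forms stay close together. The CP form does not. At t = 0.44 an interim Z of 0.2 stops the trial on the Z boundary and continues it on the CP boundary. At t = 0.556 a Z of 0.30 does the reverse.

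**The case against.** The strongest reply is that little depends on this. The passage giving the six-week trigger is about the proposed sample size, so the enrolled patients are naturally the planned total, and half enrolment may be shorthand for the same midpoint. Two values of N do not move the fraction unless the look is set from one and the final analysis from the other, and no passage says that 40 completers of 72 is intended. Counting completers only is also pessimistic: crediting partial visits raises 0.44 to about 0.47, with power 84.3%. At 0.44 the chance that the interim Z falls between the B and drift cut-offs is about 1.2% under the null and 0.3% under the design drift. Finally, CP and Z disagree even at 0.5, so timing is not the source of that mismatch.

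Most of this stands, and it limits the point to a minor one. Two things remain. The shorthand reading is nowhere stated, and the sample size paragraph does attach its power to 80 while the stopping rule uses 72. The CP rule, which the plan lists first, is sensitive to timing, and its disagreement with Z at 0.5 is a further reason to name one governing boundary.

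The weights for the arm-dropping test in rule 1b are not at risk: both wordings plan a 50% look, and weights fixed from that do not depend on N.

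**Conclusion.** The contradiction in the trigger and in N is real and should be reconciled; its severity is minor. With Z 0.253 fixed, a fraction between 0.44 and 0.556 changes power by well under one point and puts the interim false-negative rate between 4.1% and 2.4%. Under the CP rule the chance of stopping under the null ranges from 43% to 64%, against the stated 60%. These figures rest on even accrual, completers only, and the 85%-power drift.

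A reader might infer more than the documents support:

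- **That the look could fall far from half information.** The lowest combination (35.5 enrolled, 31.4 completers, final N of 80) gives t = 31.4/80 = 0.39, with power 83.3% and an interim false-negative rate of 5.2%. Larger shifts need a dropout rate, and none is stated.
- **That the trigger could be met at about 8 enrolled.** This takes the enrolled patients as those enrolled to date; the planned total is the natural reading.
- **That every boundary figure was computed at 0.5.** The CP value of 0.30 does not reproduce there.
- **That 71 against 72 matters.** As totals, both approximate, they move the fraction by less than 0.01 (35.5/72 = 0.493). The conflict that counts is 72 against 80.

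**What to change.** 1. State one planned N, 72 or 80, throughout, and tie the power statement to it.
2. Define the trigger once as a fixed count: for example, when the first 36 of 72 randomised subjects have reached Week 6 or left, with the interim analysis limited to those 36.
3. Name one governing futility boundary. Reconcile the CP and Z values at that fraction, stating the drift under which CP is computed.
4. State that the boundary will be recomputed if the observed information fraction differs from plan.

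Items 1 and 2 are changes of wording. Item 3 is more than that: Z 0.253 corresponds to CP 0.351, so keeping Z alone would change the stated CP threshold, and keeping CP below 0.3 would change the Z cut-off. The choice should be made and documented before any unblinded look. The operational cost is that the look comes about six weeks later than at 36 enrolled, with about 4 more subjects randomised by then.

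### The stated 60% chance of a futility stop under the null fits a pooled-only rule; with the dose-level check in items 1a and 1b, a full stop has probability of about 44% to 52%

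*Combined protocol and SAP*

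**What the plan says.** Section 9, Futility Interim Analysis Plan, derives its boundary "with 60% (P_{L0}) chance of stopping for futility under the null hypothesis". From that input it obtains a final critical value of 1.947 (P ≤ 0.0515) and 84.6% power, reported as "15.4% overall Type II error rate with 3.1% false negative error rate at interim look" plus 12.3% at study end.

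The numbered stopping rule follows. Item 1 is "A recommendation to stop the trial for futility if CP value for comparing combined oxytocin vs. placebo" is below 30%, and it adds: "An equivalent boundary for interim Z-test value is 0.253 (interim P>0.800"). Item 1a applies once the combined group has met that criterion: "we will examine CP and interim Z-test value for each dose (vs. placebo) to check if both dose groups meet a similar stopping criterion". The criterion is given in two forms, conditional power below 0.3 or P>0.800, and is tied to an adjusted power of 80%. Item 1b begins "In case of dropping only 1 dose arm and reallocation of remaining subjects to another arm" and prescribes a fixed weighted Z-test for that case.

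The Sample Size Calculation sets the allocation: "An estimated sample size of 24 in the placebo group and 48 in the oxytocin group (24 in each dose group").

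**The concern.** The operating characteristics and the stopping rule appear to describe different procedures. If pooled futility alone ended the trial, items 1a and 1b would have nothing to decide. They serve a purpose only if a trial that is futile on the pooled comparison can still continue on one dose. The event that ends the trial is then smaller than the event whose probability is printed.

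The plan excludes early stopping for efficacy, so ending an unpromising trial early is a main purpose of the look. Anyone judging what the look is worth, or how encouraging a decision to continue is, would rely on a stopping rate that does not belong to the rule being applied.

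**Working it through.** **Inputs.** Pooled boundary Z = 0.253, final critical value c = 1.947 and information fraction t = 0.5 (Futility Interim Analysis Plan and Sample Size Calculation). Two-sided alpha 0.05, 85% power, arms of 24/24/24 (Sample Size Calculation). Pooled design drift θ = 1.960 + 1.036 = 2.996.

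**Reproducing the printed figures with a pooled-only rule.**
- Null stop: Φ(0.253) = 0.600. The two-sided P is 0.800, B = 0.253 × √0.5 = 0.179, and the drift estimate is 0.253/√0.5 = 0.358.
- Interim false negative: Φ(0.253 − 2.996 × 0.7071) = Φ(−1.866) = 0.031.
- From the bivariate normal of interim and final Z (correlation √0.5): power 0.846, failure at study end 0.123, and upper-tail alpha at 1.947 of 0.0250.

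These match the plan's 60%, 3.1%, 84.6%, 12.3% and 1.947. No dose-level check enters any of them.

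**The two-step rule.** With equal arms and a shared placebo group, the two dose statistics Z₁ and Z₂ have correlation 0.5. The variance of their sum is 1 + 1 + 2 × 0.5 = 3, so Z_pooled = (Z₁ + Z₂)/√3. A full stop needs Z_pooled ≤ 0.253 and both Z₁ and Z₂ ≤ b, where b is the per-dose boundary. If both doses exceeded 0.253, the pooled Z would exceed 2 × 0.253/√3 = 0.292. So when the pooled comparison is futile and there is no full stop, exactly one dose has escaped.

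**Choice of b.** Item 1a gives two forms of the criterion.
- P>0.800: b = 0.253.
- Conditional power below 0.3: b = (c − z₀.₇₀√(1−t) − θ_d(1−t))/√t. The dose-level drift θ_d is the pooled drift times √0.75 = 0.866, because 1/24 + 1/48 = 0.0625 and 1/24 + 1/24 = 0.0833.
  - 85%-power drift: θ_d = 2.996 × 0.866 = 2.595, so b = (1.947 − 0.371 − 1.297)/0.7071 = 0.39.
  - 80%-power drift: θ_d = 2.802 × 0.866 = 2.426, so b = (1.947 − 0.371 − 1.213)/0.7071 = 0.51.

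**Null results, pooled boundary kept at 0.253** (numerical integration; the first two rows were also checked by simulation with 3 million replicates):

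| Per-dose criterion | b | Full stop | Continue on one dose | Shortfall from 60% |
|---|---|---|---|---|
| P>0.800 | 0.253 | 43.9% | 16.1% | 16 points |
| CP<0.3, 85%-power drift | 0.39 | 49.0% | 11.0% | 11 points |
| CP<0.3, 80%-power drift | 0.51 | 52.3% | 7.7% | 8 points |

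If each dose is instead taken to have 80% power in its own right (drift 2.80), b = 0.248 and the full stop is 43.7%, close to the first row.

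**Alternative (85%-power drift, both doses equally active, b = 0.253).** Pooled futility 3.1%, full stop 1.5%, one-dose continuation 1.7% (rounded separately).

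**The case against.** The strongest reply is that the two-step rule is inferred. The text that derives the boundary, and item 1 taken alone, recommend stopping on the pooled comparison, and 60% is exactly right for that rule. Item 1a says only that the doses will be examined, and no sentence says the trial continues when one dose is not futile. This stands as a limit: the arithmetic for the pooled rule is correct, and the fault is that the stopping rule goes on to add a branch the figures leave out. It does not remove the point, because item 1b supplies a test for a trial that drops one dose and continues.

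The reply also rightly limits the size. A reader might infer that the written rule stops an inert drug 44% of the time, full stop. The documents do not support a single figure, because item 1a offers two criteria that give different boundaries, and its reference to 80% power opens the reading that gives 52%. A further mismatch also exists: Z = 0.253 corresponds to conditional power of 0.35, not 0.30, at the 85%-power drift. That is a separate matter, and no part of the 8 to 16 points comes from it.

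Three other inferences go too far.
- That Type I error is inflated by a known amount. Upper-tail alpha at 1.947 under the two-step rule (b = 0.253) simulates at about 0.0254 or 0.0278, depending on whether the weighted test carries forward the pooled or the better dose's first-stage statistic. This assumes that all remaining oxytocin places go to the retained dose. The plan specifies neither.
- That early stopping is the look's only use. The plan also gives dropping a dose and checking design assumptions as uses.
- That a specific number of patients is saved or lost. The look is triggered by completion of six weeks' follow-up and no enrolment pause is stated, so the number already enrolled at that time is unknown.

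**Conclusion.** The point holds as a mismatch between the stated operating characteristics and the stopping rule. The direction is certain once items 1a and 1b are given effect, because a full stop is a subset of pooled futility. Under the null, the printed 60% is about 8 to 16 points too high: a full stop has probability of about 44% to 52%, according to the per-dose criterion. Under the 85%-power alternative at b = 0.253, the printed 3.1% overstates the false-negative rate for a full stop, which is about 1.5%. On that side the printed figure is conservative.

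These results assume equal arms at the interim, half information, normal test statistics, the printed pooled boundary of 0.253, and a trial that continues whenever one dose escapes its boundary.

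**What to change.** In the stopping rule, state that a full stop requires the pooled comparison and both dose comparisons to be futile, that the trial otherwise continues on one dose, and which single per-dose criterion governs. Then, in the text that derives the boundary, replace the 60% and 3.1% with the probabilities of a full stop, one-dose continuation and two-dose continuation, under both the null and the alternative. Recompute the linked figures (1.947 and 0.0515, 84.6%, 12.3%) for the same rule. This also means stating which first-stage statistic the weighted Z-test uses. Inserting new stopping rates beside a critical value derived from 60% would not be enough.

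The alternative is to delete items 1a and 1b, so that pooled futility stops the trial and the printed 60% and 3.1% hold; the option of continuing on one dose is then lost.

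The first route costs a re-run of the operating characteristics, some redrafting, and a less favourable stated chance of early stopping. Neither route adds patients or procedures.
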